8.2.5.5 Summaries of Baseline Characteristics, Demographics, and Other Analyses

Demographic variables (e.g., age, gender), baseline characteristics, primary and secondary diagnoses, and prior and concomitant therapies will be summarized by descriptive statistics or categorical tables. The number and percentage of subjects screened, randomized, the primary reasons for screening failure, and the primary reason for discontinuation will be displayed.

8.2.6 Multiplicity

There will be no multiplicity control across the primary and secondary endpoints tests in this study or across the interim and final analysis.

8.2.7 Sample Size and Power Calculations

If the true hazard ratio is 0.5, the study will need approximately 74 PFS events to have 80% power to reject a null hypothesis of equal PFS distributions in the two groups at one-sided 0.025 Type I error. Approximately 120 subjects will be randomized in 1:1 ratio to accumulate this number of events with 0.5-year enrollment period and 2-year total study duration assuming the median PFS in the (PBO+D+T) group is 10 months (rounded up estimate of 9.4 months provided in Flaherty et al. paper [101]) and yearly dropout rate is 5%.

The observed hazard ratio needs to be approximately 0.62 or lower for the treatment effect to be statistically significant. This ratio translates to approximately 6.2 months increase in median duration.

8.2.8 Subgroup Analyses and Effect of Baseline Factors

The hazard ratio estimate and its 95% confidence interval for PFS and the ORR estimate and its 95% CI will be provided in the subgroups of subjects who are PD-L1 positive and PD-L1 negative. In addition, we will explore the treatment effect on the PFS (hazard ratio estimates and 95% CI) within each of the following subgroups: Age (≤ 65 vs. > 65 years), Sex (female vs. male), Race (white, non-white), ECOG status (0 vs. 1), LDH ($>1.1 \times \text{ULN}$ vs. $\leq 1.1 \times \text{ULN}$). The consistency of the treatment effect will be assessed descriptively via summary statistics by category for the classification variables listed above. The number of subjects in each subgroup and the number (percent) of subjects with the PD will be also provided by treatment group. If a subgroup has no subjects with the PD in at least one of the treatment groups, the hazard ratio estimate and its 95% CI will not be derived.

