5.2.5 Treatment Duration

Subjects who have a confirmed complete response after at least 6 months of study treatment and 2 doses of pembrolizumab treatment beyond CR may stop pembrolizumab at the investigator's discretion. Trametinib and/or dabrafenib treatment may be continued until PD or unacceptable toxicity or until completion of 24 months of treatment.

All subjects who continue pembrolizumab treatment to 24 months and who did not discontinue prior to 24 months due to PD or unacceptable toxicity will discontinue pembrolizumab at that time. Beyond 24 months, trametinib and/or dabrafenib treatment may be continued off study as per standard of care.

The Part 3 final analysis did not demonstrate a statistically significant increase in PFS in the experimental arm compared to the control arm. Subjects in the Part 3 experimental arm experienced a higher rate of Grade 3-5 AEs, SAEs, and discontinuations due to AEs compared to the control arm. Therefore, there is no further rationale to offer re-challenge with triplet therapy and Second Course treatment will not be offered to any subject in KEYNOTE-022. In exceptional cases and upon Sponsor consultation and approval, trametinib and/or dabrafenib may be continued on study after completion of 24 months of treatment with pembrolizumab combined with trametinib and dabrafenib or placebo combined with trametinib and dabrafenib. These subjects can continue in accordance with the flow chart in Section 6.2 until the study is closed by the Sponsor. At the time of study closure, the subjects would move to local supply and continue care under their local treating physician.

In the event a Part 3 subject discontinued study treatment due to documented disease progression, and the unblinding of treatment alters a subject's eligible therapy options outside of the trial, a PI may request to have the subject's treatment assignment unblinded after discussion with Sponsor. All precautions will be taken to ensure the Sponsor and blinded site personnel remain blinded to the subject's treatment.

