8.1.3 Part 3: Pembrolizumab in Combination with Trametinib and Dabrafenib

8.1.3.1 Final Efficacy Analyses

The primary analysis population in Part 3, Intent-to-Treat Set (ITT), will include all randomized subjects. Primary endpoint in Part 3 is the Progression-Free Survival (PFS) per RECIST 1.1 defined as the time from randomization to the first documented disease progression or death due to any cause, whichever occurs first. The treatment groups will be compared in PFS by stratified log-rank test. While the randomization is stratified by ECOG PS (0 vs. 1) and LDH ($>1.1 \times \text{ULN}$ vs. $\leq 1.1 \times \text{ULN}$), due to a very low number of subjects enrolled in the stratum ECOG=1 and LDH $\leq 1.1 \times \text{ULN}$, the two strata with ECOG=1 (ECOG=1 and LDH $\leq 1.1 \times \text{ULN}$; ECOG=1 and LDH $>1.1 \times \text{ULN}$) will be combined for all analyses. A Cox proportional hazard model stratified using the same strata with Efron's method of tie handling will be used to estimate the hazard ratio and its 95% confidence interval. The Kaplan-Meier method will be used to estimate the PFS survival curve.

Secondary endpoints include objective response rate (ORR) per RECIST 1.1, response duration per RECIST 1.1, and overall survival (time to death).

The analysis strategy for primary and efficacy endpoints are provided in [Table 38](#).

Table 38 Analysis Strategy for Primary and Secondary Efficacy Endpoints in Part 3

Endpoint (Description, Time Point)	Approach [†]	Statistical Method [‡]	Analysis Population	Missing Data Approach
Progression-free-survival	P	Testing: Stratified Log-rank test Estimation: Stratified Cox model with Efron's tie handling method Kaplan-Meier method for PFS curve estimation in each treatment group	ITT	Censored at last assessment
Objective response rate	S	Stratified Miettinen and Nurminen method [100]	ITT	Subjects with missing data are considered as non-responders
Response Duration	S	Summary statistics using Kaplan-Meier method	All responders	Non-responders are excluded in analysis
Overall survival	S	Summary statistics using Kaplan-Meier method	ITT	Censored at last date
† P=Primary , S=Secondary				

8.1.3.1.1 Power of the Final Efficacy Analysis of Part 3

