8.2.3.1.1 Primary Endpoint

Progression-free Survival (PFS): is defined as the time from randomization in Part 3 (or the start of treatment in other Parts) to progressive disease (PD) or death, whichever occurs earlier, based upon RECIST 1.1 by the investigator review. Subjects without documented PD/death will be censored at the last disease assessment date.

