For PFS, subjects without documented PD/death will be censored at the last disease assessment date or, if they started new anti-cancer treatment, at the last disease assessment before initiation of the new anticancer treatment (Table 40). Two sensitivity analyses of PFS will be performed. The rules for defining the time of progression or censoring in the primary and two sensitivity PFS analyses are provided in Table 41.

Table 41 Censoring Rules for Primary and Sensitivity Analyses of PFS

Situation	Primary Analysis	Sensitivity Analysis 1	Sensitivity Analysis 2
No PD and no death; new anticancer treatment is not initiated	Censored at last disease assessment	Censored at last disease assessment	Censored at last disease assessment if still on study therapy; progressed at treatment discontinuation otherwise
No PD and no death; new anticancer treatment is initiated	Censored at last disease assessment before new anticancer treatment	Censored at last disease assessment before new anticancer treatment	Progressed at date of new anticancer treatment
PD or death documented after ≤ 1 missed disease assessment	Progressed at date of documented PD or death	Progressed at date of documented PD or death	Progressed at date of documented PD or death
PD or death documented after ≥ 2 missed disease assessments	Progressed at date of documented PD or death	Censored at last disease assessment prior to the ≥ 2 missed disease assessment	Progressed at date of documented PD or death

ORR will be estimated as the percentage of responders among subjects in each treatment group. 95% CIs for within-group ORRs will be provided using the Clopper-Pearson method [102]. The treatment comparison between arms will be based on Miettinen and Nurminen's method [100] based on difference in proportions stratified using strata from the PFS analysis.

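### Section 8.2.8 counts PD only, and withholds the subgroup hazard ratio when an arm has no PD, although a PFS event is PD or death

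*Combined protocol and SAP*

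**What the plan says.** The subgroup effect measure is a PFS hazard ratio. Section 8.2.8 calls for it in the PD-L1 positive and negative subgroups, and then says "we will explore the treatment effect on the PFS (hazard ratio estimates and 95% CI) within each of the following subgroups", listing age, sex, race, ECOG status and LDH. Two supporting rules follow. On counts: "the number (percent) of subjects with the PD will be also provided by treatment group". On withholding: "If a subgroup has no subjects with the PD in at least one of the treatment groups, the hazard ratio estimate", with its interval, is not derived. Neither rule mentions death.

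The endpoint is a composite. Section 8.2.3.1.1 measures PFS from randomization in Part 3 "to progressive disease (PD) or death, whichever occurs earlier, based upon RECIST 1.1 by the investigator review". Section 8.1.3.1 says the same for Part 3: "the first documented disease progression or death due to any cause, whichever occurs first". Table 41 in Section 8.2.5.1 treats a death as an event in the primary analysis ("Progressed at date of documented PD or death") and names the two components separately ("No PD and no death; new anticancer treatment is not initiated").

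**The concern.** The count beside a hazard ratio should be the number of events the model used, because readers judge from it how much information the estimate carries. A PD-only count falls short of that number wherever a subject died without documented PD.

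The withholding rule has the same mismatch. A PFS hazard ratio cannot be usefully estimated when an arm has no PFS event, and that is a sound reason to withhold it. Having no PD is a different condition. An arm whose events are all deaths still contributes events to the model.

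What is at stake is the accuracy of descriptive subgroup tables. Section 8.2 says no separate SAP will be issued, so the wording of 8.2.8 is what a programmer would follow.

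**Working it through.** **Text check.** The plan gives no figure on this point, so the first step is to compare uses of the term.

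- Sections 8.2.3.1.1 and 8.2.5.1 write PD and death together when the composite is meant.
- Section 8.2.3.1.2 ends response duration at progression alone, without death.
- Section 8.2.3.1.3 gives PD a further meaning: the ordinal response places several kinds of discontinuation in the PD category.
- No section defines PD to include death. Section 8.1.4, the summary of the subgroup analyses, mentions no counts.

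**Size of the count gap.** Let q be the share of first PFS events that are deaths without prior PD. The documents do not give q, so 5% to 30% is assumed. Against the 74 planned events (Section 8.2.7), the PD-only total is 74 × (1 − q): 70.3, 66.6, 59.2 and 51.8 for q = 5%, 10%, 20% and 30%. The shortfall is therefore about 4 to 22 events across the whole trial. How it would divide among subgroups is unknown.

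**Is the withheld hazard ratio estimable?** In an invented subgroup of 8 per arm, arm A has 2 PFS events, both deaths, and arm B has 6 (5 PD, 1 death). Section 8.2.8 read literally would show 0 versus 5 and no hazard ratio. A Cox model with Efron ties on the 2 versus 6 PFS events gives 0.28 (95% CI 0.06 to 1.39). This is finite, though imprecise. One event in each arm is normally enough for a finite estimate, but not when the event times are fully separated.

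**How often would this happen?** Inputs from Section 8.2.7: control median 10 months, hazard ratio 0.5 (so triplet median 20 months under exponential PFS), 6-month enrollment, 24 months in total, 5% yearly dropout, and 60 subjects per arm (120 randomized 1:1).

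- Event probability for one subject: p = average over follow-up u, uniform on 18 to 24 months, of λ/(λ+η) × [1 − exp(−(λ+η)u)], with λ = ln 2/median and η = −ln(0.95)/12.
- Expected events are 44.4 (control) and 29.8 (triplet), in total 74.1, which agrees with the plan's 74. Dividing by 60 gives p = 0.739 and 0.496.
- With n per arm, an arm has no PFS event with probability (1 − p)^n, and no PD with probability (1 − p(1 − q))^n.
- P(withheld although both arms have an event) = P(both arms have a PFS event) − P(both arms have a PD).

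Example, n = 3 and q = 30%: no PD has probability 0.278 (triplet) and 0.112 (control); no event has 0.128 and 0.018. So (1 − 0.128)(1 − 0.018) − (1 − 0.278)(1 − 0.112) = 0.857 − 0.641 = 0.216.

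| Subjects per arm | q = 5% | q = 10% | q = 20% | q = 30% |
|---|---|---|---|---|
| 3 | 2.7% | 5.7% | 12.9% | 21.6% |
| 5 | 1.0% | 2.2% | 5.7% | 10.8% |
| 8 | 0.2% | 0.5% | 1.4% | 3.2% |
| 10 | 0.1% | 0.2% | 0.5% | 1.4% |
| 15 | <0.1% | <0.1% | <0.1% | 0.2% |

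**The case against.** The strongest reply is that PD in 8.2.8 is shorthand for a PFS event. The two sentences follow directly on the PFS hazard ratios, and Table 41 itself labels a death as progressed. This is plausible and may be what was intended. But the text does not say so: the same table separates PD from death, and the plan uses progression without death elsewhere. The shorthand reading stands as a likely explanation and does not settle what the tables count.

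It can also be said that nothing turns on this. The analyses are exploratory, consistency is assessed descriptively, and an estimate like the one in the invented example tells the reader little. Section 8.2 allows changes to exploratory analyses to be listed in the CSR, and Section 5.2.5 reports that the Part 3 final analysis has been done. All of that stands, and it limits the weight of the point.

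A reader might infer more: that PD-only counts flatter the triplet, since Section 5.2.5 reports "Subjects in the Part 3 experimental arm experienced a higher rate of Grade 3-5 AEs, SAEs, and discontinuations due to AEs". The documents do not support this. That statement gives no deaths by arm, and Grade 3-5 does not isolate fatal events. The hazard ratio beside the count already includes deaths. Mortality is also shown elsewhere: death is a Tier 2 item with a between-arm CI in Table 42, and OS is compared by stratified log-rank test in Section 8.2.5.1.

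A reader might also infer that every subgroup count is wrong, or that particular subgroups are small enough for the withholding rule to matter. Counts differ only where a death without PD occurs. The only cell the plan calls very small is ECOG 1 with LDH at or below 1.1 × ULN, which is a randomization stratum and not an 8.2.8 subgroup.

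**Conclusion.** Section 8.2.8 is wrong as written, with minor consequences. Its count and its withholding rule use PD, while the hazard ratio they accompany uses PD or death. The count mismatch can arise in any subgroup that includes a death without documented PD. Wrongful withholding is realistic only with roughly 3 to 8 subjects per arm, and is under 0.2% with 15.

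These figures rest on an assumed death share of 5% to 30%, taken as equal in both arms, and on the planning medians holding within the subgroup. The documents give neither the share nor the subgroup sizes. The primary PFS test and the subgroup hazard ratios that are derived do not change.

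**What to change.** In both sentences of 8.2.8, replace the reference to subjects with PD by *subjects with a PFS event (PD or death)*. The displayed count then matches the model, and the hazard ratio is withheld only when an arm has no PFS event. If the Part 3 subgroup tables already count PFS events, a sentence in the CSR saying so is enough. If they count PD only, the CSR should record the correction and the tables should be rerun. Splitting the count into PD and death without PD is optional.

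The cost is a change of a few words and, at most, a rerun of the subgroup tables. No new data are needed.

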8.2.9 Interim Analyses

Interim analysis of Part 3 will be conducted to inform potential early Go/No Go decision for initiation of Phase III study before the completion of Part 3. The data from the first 80 subjects randomized into the study will be used in the interim analysis. The interim analysis will be conducted when the first 80 subjects randomized into the study will have completed their Week 36 visit and have their central radiology assessment at Week 36 available or have discontinued prior to Week 36.

8.2.9.1 Primary Endpoint for the Interim Analysis

The primary endpoint for the interim analysis is the ordinal response at Week 36 with the following five categories: CR, VGPR, MPR, SD, and PD determined by central review. Subjects who discontinued prior to Week 36 will be assigned to one of these categories for Week 36 according to their reason for discontinuation (see the endpoint definition).

8.2.9.2 Analysis of the Primary Endpoint for the Interim Analysis

The two treatment groups will be compared in the primary endpoint by Analysis of Variances (ANOVA) on scores 1 to 5 assigned to the response categories: CR=1, VGPR=2, MPR=3, SD=4, PD=5. ANOVA will include factors for treatment group and the strata from the PFS analysis. The variances in the two treatment groups will be allowed to be unequal. The desired effect of the addition of pembrolizumab to the (PBO+D+T) combination is to shift the ordinal response towards lower scores [lower the treatment group mean of (MK+D+T) compared to (PBO+D+T)].

8.2.9.2.1 Interim Decision Rules

If analysis of the ordinal response at Week 36 results in a statistically significant comparison in favor of the (MK+D+T) combination at one-sided Type I error of 0.025, the decision to

initiate Phase III study without waiting for PFS results will be considered. If the analysis shows that (MK+D+T) is worse than (PBO+D+T) at one-sided 0.05 Type I error, the futility will be established and the decision not to initiate a Phase III study may be considered.

8.2.9.2.2 Power of the Interim Analysis

The true mean of the ordinal endpoint at Week 36 in the high dose dabrafenib and trametinib combination treatment group in Flaherty et al. study [101] is projected to be 3.51 (an average of Week 32 and Week 40 means in Flaherty et al. study [101]). The following assumptions were used to derive the distribution of the ordinal endpoint at Week 36 in (MK+D+T) treatment group. We assumed that the subjects in (MK+D+T) treatment group reach their Best Overall Response by Week 36 and retain it at Week 36. We further assumed that the Best Overall Response in subjects in the (MK+D+T) treatment group is the same as the Best Overall Response in the high dose dabrafenib and trametinib combination treatment group in the Flaherty et al. study [101]. Therefore, the assumed distribution of the ordinal endpoint at Week 36 in (MK+D+T) treatment group matches the distribution of the Best Overall Response in the high dose dabrafenib and trametinib combination treatment group in the Flaherty et al. study [101], with the mean of 2.59. Thus, the true between-treatment difference in the mean ordinal response under the alternative hypotheses is 0.92; the standard deviation that corresponds to the specified distributions of the ordinal response at Week 36 is approximately 1.29. Under the null hypotheses (the ordinal response in the (MK+D+T) treatment group at Week 36 is the same as in the (PBO+D+T) treatment group), the true difference in means is 0 and the standard deviation is 1.53.

Power for Superiority Decision

With 40 subjects per treatment group, between-treatment difference of 0.92 and standard deviation of 1.29, the interim analysis has approximately 88% power to establish superiority of (MK+D+T) in ordinal response at Week 36. The smallest difference in treatment means detectable at one-side 0.025 Type I error is approximately 0.57 (with the mean in the (MK+D+T) treatment group lower than the mean in the (PBO+D+T) treatment group).

Observed Difference Required for Futility Decision

With 40 subjects per treatment group and standard deviation of 1.53, the observed difference in the treatment means of the ordinal response should be at least 0.56 (with mean in the (MK+D+T) treatment group higher than the mean in the (PBO+D+T) treatment group) to reject the null hypothesis of the equal means at one-sided 0.05 Type I error.

Interpretation of the Difference in the Means of the Ordinal Endpoint

The difference of 0.57 in the treatment group means can be achieved if, for example, the responses of 57% of subjects in one treatment group are moved one category down on the ordinal scale (VGPR to CR, or MPR to VGPR, or SD to MPR, or PD to SD); or the responses of 20% of subjects are moved 2 categories down (from MPR to CR, or SD to

VGPR, or PD to MPR) and the responses of another 17% of subjects are moved one category down.

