8.2.5 Statistical Methods

8.2.5.1 Statistical Methods for Efficacy Analyses

Parts 1, 2, 4 and 5 in Subjects Treated with (MK+D+T) or (MK+T)

The best overall response and PFS based on the investigator review per RECIST 1.1 in subjects along with baseline characteristics will be listed. Percentage of subjects that attained Objective Response will be estimated.

Part 3

The analysis strategy for primary and secondary endpoints in Part 3 is summarized in [Table 40](#).

Table 40 Analysis Strategy for Primary and Secondary Efficacy Endpoints in Part 3

Endpoint (Description, Time Point)	Approach [†]	Statistical Method [‡]	Analysis Population	Missing Data Approach
Progression-free-survival	P	Testing: Stratified Log-rank test Estimation: Stratified Cox model with Efron's tie handling method Kaplan-Meier method for PFS curve estimation in each treatment group	ITT	Censored at last assessment
Objective response rate	S	Stratified Miettinen and Nurminen method [100]	ITT	Subjects with missing data are considered as non-responders
Response Duration	S	Summary statistics using Kaplan-Meier method	All responders	Non-responders are excluded in analysis
Overall survival	S	Summary statistics using Kaplan-Meier method	ITT	Censored at last date
[†] P=Primary , S=Secondary				

Primary endpoint in Part 3 is PFS. The treatment groups will be compared in PFS by stratified log-rank test. While the randomization is stratified by ECOG PS (0 vs. 1) and LDH (>1.1xULN vs. ≤1.1xULN), due to a very low number of subjects enrolled in the stratum ECOG=1 and LDH ≤1.1xULN, the two strata with ECOG=1 (ECOG=1 and LDH ≤1.1xULN; ECOG=1 and LDH >1.1xULN) will be combined for all analyses. A Cox proportional hazard model with a factor for treatment group stratified using the strata above with Efron's method of tie handling will be used to estimate the hazard ratio and its 95% confidence interval. The Kaplan-Meier method will be used to estimate the PFS survival curve, the median PFS and its 95% CI, PFS at 44 weeks (10.1 months) and its 95% CI, and PFS at 74 weeks (17 months) and its 95% CI will be estimated. The time points chosen for estimation are close to the expected time of median PFS in the (PBO+D+T) treatment group (44 weeks) and the respective smallest detectable median in the (MK+D+T) treatment group. Both time points are placed 2 weeks after the scheduled visit as lower variability of the Kaplan-Meier estimate is expected outside of the clinic visit window.

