8.2.9.2.3 Secondary and Exploratory Endpoints at the Interim Analysis

Secondary endpoints at the Interim Analysis

- 1) Percentage of subjects with Deep Response (DR) at Week 36 defined as either CR or VGPR at Week 36
- 2) Percentage of subjects with CR at Week 36
- 3) Ordinal response at Week 36 with the following five categories: CR, VGPR, MPR, SD, and PD determined by the investigator review

Exploratory endpoints at the Interim Analysis

- 1) Percentage of subjects with PR at Week 36
- 2) Best Overall Response (analyzed as an ordinal endpoint)
- 3) Best Percent Reduction in Tumor Line Length by Week 36
- 4) Percentage of subjects with sustained response at Week 36 -subjects who achieved response (confirmed CR or PR) prior to Week 36 but have not yet progressed at Week 36
- 5) Tumor growth kinetics endpoints: growth rate constant (GST) and time-to-growth (TTG)

Analysis of Secondary and Exploratory Endpoints

Binary secondary and exploratory endpoints will be compared between the two treatment groups by Fisher's exact test. All analyses will be performed at two-sided Type I error 0.05; there will be no control of Type I error across the primary and secondary hypotheses.

Summaries of the ordinal response (based on investigator review) distribution by week, including frequencies of categories and the mean response, will be provided.

A sensitivity analysis of the ordinal response at Week 36 based on the investigator review will be performed using the analysis described for the ordinal response at Week 36 based on central review.

Power of the Analyses of Secondary Endpoints at the Interim Analysis

If the true percentage of subjects with CR at Week 36 in (PBO+D+T) group is 10% (approximate expected percentage) and the true percentage of subjects with CR at Week 36 in (MK+D+T) group is 35%, the power for comparison of the percentages of subjects with CR at Week 36 is 71%. If the true percentage of subjects with DR at Week 36 in (PBO+D+T) group is 37.5% (approximate expected percentage) and the true percentage of

subjects with CR at Week 36 in (MK+D+T) group is 70%, the power for comparison of the percentages of subjects with CR at Week 36 is 79%.

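### Does the 88% interim power contradict the hazard ratio of 0.5 on which Part 3 was sized?

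*Combined protocol and SAP*

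**What the plan says.** Section 8.2.9.2.2 takes a control mean of 3.51 for the five-category score at Week 36 from the published doublet trial. For the triplet it says "We assumed that the subjects in (MK+D+T) treatment group reach their Best Overall Response by Week 36 and retain it at Week 36", and it sets those best responses equal to the doublet's, which gives a mean of 2.59. With a difference of 0.92, an SD of 1.29 and 40 subjects per arm, "the interim analysis has approximately 88% power to establish superiority of (MK+D+T) in ordinal response at Week 36". It adds that "The smallest difference in treatment means detectable at one-side 0.025 Type I error is approximately 0.57", and then explains that difference as shifts between response categories.

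Section 8.2.7 sizes the final analysis on a different endpoint, investigator-read PFS: "If the true hazard ratio is 0.5, the study will need approximately 74 PFS events to have 80% power", and "Approximately 120 subjects will be randomized in 1:1 ratio to accumulate this number of events with 0.5-year enrollment period and 2-year total study duration". The control median is 10 months, in line with 8.2.5.1: "The time points chosen for estimation are close to the expected time of median PFS in the (PBO+D+T) treatment group (44 weeks").

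Section 8.2.9.2.3 gives two further power figures for secondary interim endpoints. The complete-response comparison supposes that "the true percentage of subjects with CR at Week 36 in (MK+D+T) group is 35"%. The deep-response comparison starts from 37.5% in the control arm, but its triplet figure is printed as "subjects with CR at Week 36 in (MK+D+T) group is 70"%.

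**The concern.** Progression drives both endpoints in the same patients. If the triplet halves the hazard of progression or death, a definite share of that arm will have progressed by Week 36, and each of those subjects scores 5. A triplet mean of 2.59 with a modest SD leaves little room for scores of 5. The SAP therefore seems to hold two incompatible views of the triplet arm and to give interim power only for the kinder one.

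At stake is how the interim result would be read. Under 8.2.9.2.1, a significant ordinal result may lead the sponsor to consider starting Phase III before PFS is known. Someone who took 88% as the power under the effect the trial was sized for could read a non-significant interim as stronger evidence against the triplet than it is.

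**Working it through.** **1. The plan's own figure.** Inputs from 8.2.9.2.1 and 8.2.9.2.2: difference 0.92, SD 1.29, 40 per arm, one-sided 0.025.

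- Standard error = 1.29 × √(2/40) = 0.288
- Noncentrality = 0.92 / 0.288 = 3.19; critical t on 78 df = 1.99
- Power from the noncentral t = 88.3% (stated: about 88%)
- Detectable difference = 1.99 × 0.288 = 0.574, or 0.565 with 1.96 (stated: about 0.57)

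**2. Largest PD share the scenario allows.** The SD under the null, 1.53, is the control arm's. Reading 1.29 as the root-mean-square of the two arms, the triplet variance is 2 × 1.29² − 1.53² = 0.987 (SD 0.994).

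On scores 1 to 5, (x − 2)(x − 3) is never negative and equals 6 at x = 5. So

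- P(PD) ≤ [0.987 + (2.59 − 2)(2.59 − 3)] / 6 = (0.987 − 0.242) / 6 = 12.4%

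If 1.29 is the triplet's own SD, (x − 1)(x − 2), which equals 12 at x = 5, gives the tighter bound:

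- P(PD) ≤ [1.664 + 1.59 × 0.59] / 12 = 2.602 / 12 = 21.7%

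The plural reference to distributions in 8.2.9.2.2 favours the first reading. Neither an arm-specific SD nor category shares are printed.

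**3. PD share under 8.2.7.** The PFS distribution is not named. Exponential PFS with medians of 10 and 20 months, 60 per arm, 6 months' uniform enrolment, 24 months in total and 5% yearly dropout gives 44.4 + 29.8 = 74.1 events, against the stated 74. The exponential reading is therefore fair.

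- Week 36 = 252 / 30.44 = 8.28 months
- Control event-free: 0.5^(8.28/10) = 0.563
- Triplet event-free: 0.5^(8.28/20) = 0.751, so 24.9% have an event

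Weibull shapes of 0.8 to 1.4 with the control median held at 10 months give 23% to 26%.

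**4. Power at about 25% PD.** This needs the response depth of the other 75%, which the documents do not give. For the control arm, CR 10% and deep response 37.5% (8.2.9.2.3) with mean 3.51 and SD 1.53 solve to MPR 11.1%, SD 4.4%, PD 47.1%. That is near the 43.7% from step 3. Taking 3.51 and 1.53 for the control throughout (Welch):

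| Depth assumed for triplet subjects not in PD | Difference | Power |
|---|---|---|
| Same as the control's | 0.62 | 46% |
| Assumed best responses, extra PD taken from SD first, then MPR | 0.68–0.70 | 54–58% |
| Assumed best responses, extra PD taken proportionally | 0.35–0.40 | 19–23% |
| CR 35% and VGPR 35% together | 1.01–1.06 | 82–86% |

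Rows two and three need category shares that are not printed. They were solved from mean 2.59, SD 0.994, the 76% response rate in 4.2.1 and an assumed CR of 5% to 10%. Row four joins two conditions that 8.2.9.2.3 states separately.

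**5. The wording slip.** Fisher's exact test at two-sided 0.05 with 40 per arm gives 79.8% power for 70% against 37.5% (stated: 79%), and 71.7% for 35% against 10% (stated: 71%). The 70% and 79% are therefore the deep-response figures, and only the label is wrong.

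**The case for a change.** The best case for a change grants the arithmetic and the disclosure. The SAP does not say that full retention is more than a hazard ratio of 0.5 would deliver. The proxy in step 3 is sound, since the PFS and ordinal assumptions nearly agree for the control arm and part company only for the triplet. Even the kinder reading of the SD stays below 25%. The true PD category is probably larger still, because 8.2.3.1.3 also scores discontinuation for adverse events, noncompliance and withdrawal of consent as PD. One sentence or a small table would cost nothing.

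Much of this stands. The 88% should not be quoted as the power under a hazard ratio of 0.5, and full retention is optimistic.

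The case for changing the plan does not stand. The PFS comparison uses investigator-read time to event, while the interim uses a centrally read score that combines depth with durability. Nothing obliges the two to share an alternative. Retention is also the stated hypothesis: 4.2.1 hopes to join the doublet's response rate to pembrolizumab's durability, and 4.2.3.1.2 picks Week 36 because doublet responses have eroded by then. A power figure tied to the hazard ratio would need a depth profile the sponsor never specified, and step 4 shows the answer running from about 19% to 86% with that choice. The 0.57 already tells a reader what is needed without any retention assumption: a true difference of that size has roughly even odds of significance, which is why the first two rows lie near 50%.

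**Conclusion.** No change to the plan. The 88% is correct for the scenario stated beside it. That scenario is more favourable than the PFS alternative: at most about 12% triplet PD at Week 36 (about 22% on the other reading of the SD), against about 25%. The comparison assumes exponential PFS, proportional hazards, and investigator-read PFS events standing in for the centrally read category. With control-like depth, power at 25% PD would be about 46%, but that rests on a profile the documents do not supply, so it does not show the 88% to be wrong.

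Nothing downstream uses the figure. The decision rules in 8.2.9.2.1 depend on observed significance and only prompt consideration. The sample size in 8.2.7 stands apart. Sections 5.2.5 and 7.1.5.3 report the Part 3 final analysis as already done, so the decision this power statement was meant to support has passed. An added scenario would alter no analysis, estimate or conclusion.

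The CR label on the 70% and 79% figures is a clerical slip. The sentence opens with the deep-response rate in the control arm and the power reproduces for deep response, so an analyst will read it correctly.
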